Appendix 5. Test Article Administration

1. *Test article preparation*

VM202 - VM202 is supplied in a sterile glass vial containing 2.5 mg of lyophilized study product. Before administration, it will be reconstituted with 5.0 mL of water for injection (WFI) for a final VM202 concentration of 0.5 mg / mL. Each reconstituted vial is only to be used for one subject. For subjects randomized to the Low Dose or High Dose arms of the study, the final doses of VM202 will be divided evenly between the Day 0 administration and the Day 14 administration. Every individual injection will be 0.5 mL. All injections administered by intramuscular injections.

Placebo - Patients assigned to either the placebo arm or the Low Dose arm will receive normal saline injections. The placebo group will receive only normal saline injections; the Low Dose arm will receive 16 injections of VM202 and 16 injections of normal saline in each leg at both injection visits. Visually, normal saline is indistinguishable from reconstituted VM202.

Table 4. Single dose preparation and delivery for Day 0 and Day 14 Visits

Treatment Arm	Number of Vials Reconstituted at each visit	Number of injections [†] / leg	Total Volume to be Injected / leg
Low Dose 8 mg/ leg Total Dose:16 mg VM202	4 Vials VM202, reconstituted with WFI	16 of VM202 16 of placebo	16 mL
High Dose 16 mg/ leg Total Dose:32 mg VM202	8 Vials VM202, reconstituted with WFI	32 of VM202	16 mL
Placebo – Normal Saline	NA – Normal Saline	32 of placebo	16 mL

[†]Injection volume for each individual injection = 0.5 mL

2. **Test material administration** – Patients will receive injections of VM202 or placebo on Day 0, and Day 14. A fine needle (e.g. 27 gauge, 1") suitable for IM injections will be used. **Both calves will be treated with 32 injections each at each visit.** Distribute injection sites evenly over the calf muscle, carefully avoiding fascia.
3. Inject the entire amount of the drug per each injection in about 3-5 seconds. Immediately after completion of injection, lightly press the injection site with the finger head in order to prevent reflux. Do not massage the injection site. An indelible marker should be used to identify each injection site.
4. **Subsequent administrations** – Subsequent administrations should also be distributed evenly over the calf, and, as much as is possible, at different injection sites. If marks made to identify previous injection sites are visible, every effort should be made to inject at alternate locations.

Appendix 6. Patient's Global Impression of Change

Patient Global Impression of Change (PGIC) Scale

Since the start of the study, my overall status is:

✓ one box only:

Very Much Improved	 1
Much Improved	 2
Minimally Improved	 3
No Change	 4
Minimally Worse	 5
Much Worse	 6
Very Much Worse	 7

Patient's Signature: _____

Date: _____

Appendix 7. Brief Pain Inventory for Subjects with Diabetic Peripheral Neuropathy (BPI-DPN)

Brief Pain Inventory (Short Form)

Date: ____/____/____

Time: _____

[figure not shown]
Visit: Day 0 (pre-Injection) Day 30 Day 60 Day 90 Month 6 Month 9

1. Throughout our lives, most of us have had pain from time to time (such as minor headaches, sprains, and toothaches). Have you had pain other than these everyday kinds of pain today?

1. Yes

2. No

2. On the diagram, shade in the areas where you feel pain. Put an X on the area that hurts the most.

3. Please rate your pain by circling the one number that best describes your pain at its worst in the last 24 hours.

0	1	2	3	4	5	6	7	8	9	10
No										Pain as bad as you can imagine
Pain										

4. Please rate your pain by circling the one number that best describes your pain at its least in the last 24 hours.

0	1	2	3	4	5	6	7	8	9	10
No										Pain as bad as you can imagine
Pain										

5. Please rate your pain by circling the one number that best describes your pain on the average.

0	1	2	3	4	5	6	7	8	9	10
No										Pain as bad as you can imagine
Pain										

6. Please rate your pain by circling the one number that tells how much pain you have right now.

0	1	2	3	4	5	6	7	8	9	10
No										Pain as bad as you can imagine
Pain										

STUDY ID #: VMDN-002

DO NOT WRITE ABOVE THIS LINE

Subject #: _____

Date: ____ / ____ / ____

Time: _____

Visit: Day 0 (pre-Injection) Day 30 Day 60 Day 90 Month 6 Month 9

7. What treatments or medications are you receiving for your pain?

8. In the last 24 hours, how much relief have pain treatments or medications provided? Please circle the one percentage that most shows how much you have received.

0% 10% 20% 30% 40% 50% 60% 70% 80% 90% 100%
 No Complete
 Relief Relief

9. Circle the one number that describes how, during the past 24 hours, pain has interfered with your:

A. General Activity

0 1 2 3 4 5 6 7 8 9 10
 Does not Completely
 Interfere Interferes

B. Mood

0 1 2 3 4 5 6 7 8 9 10
 Does not Completely
 Interfere Interferes

C. Walking Ability

0 1 2 3 4 5 6 7 8 9 10
 Does not Completely
 Interfere Interferes

D. Normal Work (includes both work outside the home and housework)

0 1 2 3 4 5 6 7 8 9 10
 Does not Completely
 Interfere Interferes

E. Relations with other people

0 1 2 3 4 5 6 7 8 9 10
 Does not Completely
 Interfere Interferes

F. Sleep

0 1 2 3 4 5 6 7 8 9 10
 Does not Completely
 Interfere Interferes

G. Enjoyment of life

0 1 2 3 4 5 6 7 8 9 10
 Does not Completely
 Interfere Interferes

Copyright 1991 [name]
 Pain Research Group
 All rights reserved

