3.3.2. EXCLUSION CRITERIA

Subjects ***will not be eligible for the study*** if any of the following criteria are present:

1. Peripheral neuropathy caused by condition other than diabetes;
2. Other pain more severe than neuropathic pain that would prevent assessment of DPN;
3. Progressive or degenerative neurological disorder;
4. Myopathy;
5. Inflammatory disorder of the blood vessels (inflammatory angiopathy, such as Buerger's disease);
6. Active infection;
7. Chronic inflammatory disease (e.g., Crohn's disease, rheumatoid arthritis);
8. Positive HIV or HTLV at Screening;
9. Active Hepatitis B or C as determined by Hepatitis B core antibody (HBcAb), antibody to Hepatitis B antigen (IgG and IgM; HBsAb), Hepatitis B surface antigen (HBsAg) and Hepatitis C antibodies (Anti-HCV) at Screening;
10. Subjects with known immunosuppression or currently receiving immunosuppressive drugs, chemotherapy or radiation therapy;
11. Stroke or myocardial infarction within last 3 months;
12. Ophthalmologic conditions pertinent to proliferative retinopathy;
13. Specific laboratory values at Screening including: Hemoglobin < 8.0 g/dL, WBC < 3,000 cells per microliter, platelet count < 75,000/mm³, Creatinine > 2.0 mg/dL; AST and/or ALT > 3 times the upper limit of normal or any other clinically significant lab abnormality which in the opinion of the investigator should be exclusionary;
14. Uncontrolled hypertension as defined as sustained systolic blood pressure (SBP) > 200 mmHg or diastolic BP (DBP) > 110 mmHg at Screening;
15. Patients with a recent history (< 5 years) of or new screening finding of malignant neoplasm except basal cell carcinoma or squamous cell carcinoma of the skin (if excised and no evidence of recurrence); patients with family history of colon cancer in any first degree relative are excluded unless they have undergone a colonoscopy in the last 12 months with negative findings;
16. Use of any opioids; subjects may be enrolled if willing and able to discontinue use of these drugs 14 days prior to starting the Daily Pain and Sleep Interference Diary and refrain from taking these drugs for the duration of the study;
17. Subjects requiring > 81 mg daily of acetylsalicylic acid; subjects may be enrolled if willing/able to switch to ≤ 81 mg daily of acetylsalicylic acid or to another medication;

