4.2.11. BRIEF PAIN INVENTORY FOR SUBJECTS WITH DIABETIC PERIPHERAL NEUROPATHY (BPI-DPN)

The brief pain inventory (BPI-DPN)^{55,56} will be self-administered during site visits on Day 0 before the treatment (injection), on Day 30, Day 60, Day 90, at 6 months and 9 months. The Questionnaire is a patient - completed numeric rating scale that assesses the severity of pain, its impact on daily functioning, and other aspects of pain (e.g. location of pain, relief from medications). The questionnaire was also modified to distinguish between pain due to DPN and pain due to other causes.

Upon completion of the questionnaire, the study coordinator will check the questionnaire for completeness. Any omissions or ambiguous answers will be clarified by the subject prior to leaving the clinic. The full Questionnaire can be found in [Appendix 7](#).

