Appendix 1. Schedule of Evaluations and Visits & Laboratory Tests by Visit

SCHEDULE OF EVALUATIONS AND VISITS

Procedure	Screening / Baseline (-60 – 0 D)	1 st Injection Day 0		2 nd Injection Day 14 ± 1 D		Day 21 ± 3 D	Day 30 ± 3 D	Day 60 ± 3 D	Day 90 ± 7 D	6 months ± 1 mo	9 months ± 1 mo	Early Withdrawal
		Pre-dose	Post-dose	Pre-dose	Post-dose							
Baseline Evaluation												
Informed Consent	✓											
Complete Medical History	✓											
Complete Physical Exam	✓											
Cancer screening [†]	✓											
Viral screening – HIV, HTLV, HBV, HCV	✓											
Urinalysis	✓											
EKG	✓											
Pregnancy test	✓											
Safety and Efficacy Parameters												
VAS	✓	✓					✓	✓	✓	✓	✓	
MNSI ^{††}	✓									✓	✓	
Symptoms of BPNS	✓									✓		
Retinal Fundoscopy	✓										✓	✓
Daily Pain and Sleep Interference Diary	✓								✓	✓	✓	
Concomitant Medications	✓	✓		✓		✓	✓	✓	✓	✓	✓	✓
Vital Signs	✓	✓	✓	✓	✓	✓	✓	✓	✓	✓	✓	✓
PGIC [*]							✓	✓	✓	✓	✓	
BPI-DPN ^{**}			✓				✓	✓	✓	✓	✓	
Serum Chemistry and Hematology	✓	✓					✓		✓		✓	✓
HbA1c	✓								✓	✓	✓	✓
Serum HGF			✓		✓		✓	✓	✓			✓ ¹
Copies of VM202 in whole blood			✓***	✓	✓***	✓	✓	✓	✓			✓ ¹
Skin biopsy		✓								✓		
Treatment												
Injection site reaction assessment			✓	✓	✓	✓	✓	✓				✓ ²
Adverse Events			✓	✓	✓	✓	✓	✓	✓	✓	✓	✓

[†] Cancer screening: chest X-ray or chest CT scan if subject has a previous history of tobacco use within 3 months; pap smear and mammogram within past 12 months (females only); PSA within past 3 month (males only); for subjects ≥ 50 years old, colonoscopy within past 10 years; for subjects with a first degree relative with colon cancer, colonoscopy within past 12 months.

^{††} MNSI - Michigan Neuropathy Screening Instrument

1. If withdrawal occurred before Day 90 Visit

2. If withdrawal occurred before Day 60 Visit

^{*} PGIC - Patient's Global Impression of Change

^{**} BPI-DPN - Brief Pain Inventory, diabetic neuropathy specific test

^{***} 2 hours after injection (± 1 hour)

SCHEDULE OF LABORATORY EVALUATIONS

Parameters	Screen	Day 0	Day 14	Day 21	Day 30	Day 60	Day 90	6 Months	9 Months	Early Withdrawal
HbA1c	✓						✓	✓	✓	✓
Serum HGF		✓ pre-injection	✓ pre-injection		✓	✓	✓			✓ (< Day 90)
VM202		✓ pre & post injection	✓ pre & post injection	✓	✓	✓	✓			✓ (< Day 90)
HTLV, HIV-1, HIV-2	✓									
Hepatitis B and C [†]	✓									
Hematology										
Hematocrit	✓	✓			✓		✓		✓	✓
Hemoglobin	✓	✓			✓		✓		✓	✓
RBC	✓	✓			✓		✓		✓	✓
WBC with differential	✓	✓			✓		✓		✓	✓

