11.3.2. BRIEF PAIN INVENTORY FOR DIABETIC PERIPHERAL NEPHROPATHY (BPI-DPN)

The pain severity and pain interference will be calculated for each subject at each required visit based on the BPI-DPN instruction. The pain severity, pain interference and their change from baseline (post-treatment – baseline) will be summarized by study visit and treatment arm using the method for continuous variables.

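### The form in Appendix 7 does not separate DPN pain from other pain, as Protocol 4.2.11 says the BPI-DPN does, so this secondary endpoint would score pain from any cause

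*Protocol*

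**What the plan says.** Protocol 4.2.11 says of the BPI-DPN: "The questionnaire was also modified to distinguish between pain due to DPN and pain due to other causes". It then identifies the instrument to be used: "The full Questionnaire can be found in" Appendix 7. The footnote to the visit schedule in Protocol Appendix 1, repeated under SAP Table 2, reads "BPI-DPN - Brief Pain Inventory, diabetic neuropathy specific test".

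The form in Appendix 7 bears the study number and tick boxes for this trial's six BPI visits (Day 0, Day 30, Day 60, Day 90, Month 6, Month 9), so it is presented as the form for use. Its printed title is the Brief Pain Inventory in its short form; DPN appears only in the appendix heading above it. The first severity item is "Please rate your pain by circling the one number that best describes your pain at its worst in the last 24 hours". The interference block opens "Circle the one number that describes how, during the past 24 hours, pain has interfered with your" and lists seven domains.

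Protocol 6.3.2 makes change in BPI-DPN, each VM202 arm against placebo, a secondary endpoint at the five post-dose visits. SAP 11.3.2 states: "The pain severity and pain interference will be calculated for each subject at each required visit based on the BPI-DPN instruction". That instruction is in neither document.

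**The concern.** The protocol claims a property for this instrument that the appended form does not have. A subject answering the form is asked about pain in general, and nothing tells the subject to leave out a painful back, hip or shoulder. If the form is used as printed, the scores reported as BPI-DPN are scores for pain from any cause.

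This matters because the bioactivity objective concerns pain in painful DPN, and the study is meant to inform later trials. A subject whose neuropathic pain improves while some other pain does not may show less change on this form than on one confined to DPN pain. A reader of Tables 7.1 and 7.2 would take the results as DPN-specific.

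**Working it through.** The documents give no SD, power or target difference for the BPI-DPN (SAP section 4 deals with the VAS and the diary), so there is no planned figure to reproduce. The check is a comparison of the description with every item on the form.

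| Item in Appendix 7 | What is asked | Names DPN or another cause? | Names a site? | Role |
|---|---|---|---|---|
| 1 | Any pain today beyond everyday kinds | No; it sets aside only minor everyday pains | No | Not a rating |
| 2 | Shade painful areas and mark the worst one | No | Yes, by diagram | Not used in the SAP |
| 3 to 6 | Worst, least, average and current pain, 0 to 10 | No, 0 of 4 | No, 0 of 4 | Severity |
| 7 and 8 | Treatments for pain, and relief from them | No | No | Not in the severity or interference scores |
| 9A to 9G | Interference in seven domains, 0 to 10 | No, 0 of 7 | No, 0 of 7 | Interference |

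Rated items for the two scores: 4 + 7 = 11. Items that name DPN, a cause or a site: 0 + 0 = 0 of 11. The assignment of items to the two scores is read from their wording, because the scoring instruction is not reproduced.

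Other wording in the plan bears on this as follows.

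- **VAS (Appendix 8) and diary (Appendix 9).** Both confine the rating to the legs below the knee, including the feet. The BPI form, although described as DPN-specific, has no such limit.
- **SAP 11.3.2.** It calculates severity, interference and their changes from baseline, and describes no step that separates pain by cause.
- **Eligibility.** Exclusion criterion 2 bars "Other pain more severe than neuropathic pain that would prevent assessment of DPN". Other pain that is milder than the neuropathic pain is therefore admissible.
- **Completeness of the text.** One figure in Appendix 7 is not shown. It is probably the body diagram of item 2. The wording of all nine items is present, so the missing figure is unlikely to alter the count.

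The direction of the effect follows from randomisation. Other pain should be spread over the arms by chance. If it does not respond to VM202, it adds variation to the scores and can pull the difference between arms toward zero. It gives no reason to expect a false positive.

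**The case against.** The strongest reply is that the form still records DPN pain. Every subject has painful DPN in both legs, leg pain for at least 6 months, a VAS of at least 40 mm and a mean diary score of at least 4, and any other pain must not exceed the neuropathic pain. That stands. A reader might infer from the mismatch that the endpoint cannot measure DPN pain at all; the documents do not support this. The form measures DPN pain mixed with whatever other pain is present.

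Eligibility also removes some people with substantial other pain: chronic inflammatory disease is excluded (criterion 7), as are users of opioids or regular COX inhibitors who will not stop (criteria 16 and 18). This reduces the problem without removing it. Item 2 asks for the worst site, so subjects whose main pain lies outside the legs could be identified. However, it records location rather than cause, and the SAP makes no use of it.

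The instruction cited in SAP 11.3.2 is not reproduced and might contain something relevant. Even so, the questionnaire is self-administered, and a scoring rule applied afterwards cannot recover a cause that the ratings did not ask about.

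Neither the generic nor the DPN-modified instrument is in the documents for comparison, so the form's identity cannot be proved item by item. Its title and 1991 copyright line, set against the 2005 validation paper that the protocol cites for a version modified for painful DPN, suggest the generic form. What is established is that the form lacks the property claimed for it.

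Finally, this is one of several secondary endpoints, and SAP sections 5 and 5.2 treat p-values as descriptive. That limits the consequence but does not resolve the contradiction.

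**Conclusion.** The point holds as a contradiction between Protocol 4.2.11 (with the schedule footnotes) and Appendix 7. Used as printed, the form yields severity and interference scores for pain from any cause: 0 of 11 rated items carry the attribution that the protocol describes, at all six visits. The likely consequence is added noise and some dilution of the arm differences on a secondary endpoint, together with a label that claims more than the form delivers.

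The dilution cannot be sized. A reader might be tempted to put a percentage on it. That would need the share of subjects with other pain, the part such pain plays in their ratings and its response to VM202, and the documents give none of these. The ratings need not add up across sites either: an item on worst pain may simply follow the worst site.

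The primary diary endpoint and the VAS are unaffected. The conclusion rests on taking Appendix 7 as the form for use, which its study number, its visit boxes and the cross-reference in 4.2.11 all indicate.

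**What to change.** Before any Day 0 baseline is collected, replace Appendix 7 with the DPN-modified version that 4.2.11 describes and cites. Its item wording should be taken from that source, since the documents do not contain it.

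If the present form is kept, delete the claim in 4.2.11 that it distinguishes DPN pain, and remove the neuropathy-specific description from the footnotes in Protocol Appendix 1 and SAP Table 2. Label the endpoint as BPI short form, pain from any cause, in Protocol 6.3.2, SAP 11.3.2 and SAP Tables 7.1 and 7.2.

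The first option costs one replaced questionnaire and appendix; the second costs text edits only. Neither adds a visit, a procedure or a subject. Timing matters: once baselines exist on the present form, changing it would break the comparison with baseline, and only relabelling would remain.

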Appendix 8. Visual Analog Scale

The VAS will be completed by the subject. The subject should be asked: “**How do you currently rate your pain in your legs (below the knee – this includes pain in your feet)?**”

The subject should be instructed to indicate his or her current level of pain in their legs by placing a single vertical line perpendicular to the horizontal line of the scale ensuring that the two lines intersect. Additionally, the subject should be instructed to not use a check mark, “x” or circle that would intersect the horizontal line of the scale multiple times. Ensure the subject understands that the mark must be only one line that is perpendicular to and intersects the scale line. The subject should complete the VAS with a fine or medium point pen; felt tip pens and pencils should not be used.

No pain | _____ | Very severe pain

The VAS should be checked for accuracy and completeness immediately after it is completed by the subject. If the subject’s mark does not intersect the line or intersects the line more than once, reinstruct the subject to modify his or her mark so it meets the appropriate criteria. Any corrections should be accompanied by the subject’s initial and date. For Day 0 , all corrections MUST be completed prior to injections; do NOT have the subject correct the scale after injections. Instead, use the data collected prior to dosing.

The VAS score (0 to 100mm) will be calculated by measuring the distance from the left end of the line (“No Pain”) along the scale to the mark made by the subject. If the mark made by the subject intersects the horizontal line of the scale multiple times and was not corrected, measure to the middle point between the two marks. If the mark made by the subject does not intersect the line of the scale and was not corrected, project the location of the mark vertically to a point on the line of the scale for the measurement.

[figure not shown]
Appendix 9. Daily Pain and Sleep Interference Diary - One Day Sample

*Please complete one form (a + b + c) each day starting on the day indicated by the clinic.
Return the completed forms to the clinic at your next visit.*

Please circle a number from 0 to 10 that best describes your status using a fine or medium point pen.

1a. _____ **DAY** (Day of week) **Date :** _____ / _____ / _____

1b. Please rate your average pain in your legs (below the knee, this includes pain in your foot) during the past 24 hours.

1c. Please rate how much your pain in your legs (below the knee, this includes pain in your foot) interfered with sleep during the past night.

Appendix 10. Symptoms of Brief Peripheral Neuropathy Screening

INSTRUCTIONS FOR RECORDING SUBJECTIVE ELICITED SYMPTOMS:

- Ask the subject to rate the severity of each symptom listed in question 1a-1c on a scale of 01 (mild) to 10 (most severe) for right and left feet, legs.
- Enter the score for each symptom in the column marked Presence/Severity.
- If a symptom has been present in the past, but not since the last visit, enter '00-Currently Absent.'
- If the symptom has never been present, enter '11-Always Been Normal.'

Always Been Normal	Currently Absent	Mild -----										Severe
11	00	01	02	03	04	05	06	07	08	09	10	

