3.3.1. INCLUSION CRITERIA

Subjects must satisfy all of the following criteria to be included in the study:

1. Age \geq 18 years to \leq 75 years;
2. Documented history of Type I or II diabetes with current treatment control (glycosylated hemoglobin A_{1c} of \leq 10.0% at Screening) and currently on oral medication and / or insulin;
3. Diagnosis of painful diabetic peripheral neuropathy in both lower extremities;
4. Lower extremity pain for at least 6 months;
5. Visual analog scale (VAS) score of \geq 40 mm at Pre-Screening (0 mm = no pain – 100 mm very severe pain);
6. Symptoms from the Brief Pain Neuropathy Screening (BPNS) is \leq 5 point difference between legs at Initial Screening;
7. The average daily pain intensity score of the Daily Pain and Sleep Interference Diary completed after medication wash-out is \geq 4 with a standard deviation \leq 2;
8. The physical examination component of the Michigan Neuropathy Screening Instrument Score (MNSI) is \geq 3 at Screening;
9. Stable treatment of diabetes for at least 3 month with no anticipated changes in medication regimen, and no new symptoms associated with diabetes; and

10. If female of childbearing potential, negative urine pregnancy test at screening and using acceptable method of birth control during the study.

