3.4.3. SCREENING (DAY -60 TO DAY 0)

Prior to full screening, subjects will give informed consent and then be initially screened using the VAS, the Symptoms portion of the BPNS and the MNSI. Only subjects with a VAS score of $\geq 40 \text{ mm}$, a ≤ 5 point difference in symptom of BPNS between legs and MNSI score of ≥ 3 will be allowed to proceed with the full screening procedures.

If the VAS, BPNS and MNSI criteria are met, the rest of screening will proceed. If applicable, the subject will be washed out of prohibited medications. During medication wash-out and prior to randomization, subject eligibility will be assessed as follows:

- Evaluation of Eligibility Criteria
- Complete Medical History
- Concomitant Medications
- Vital Signs, including height
- Complete Physical Exam,
- EKG
- HbA1c
- Serum chemistry and hematology
- Urinalysis
- Urine pregnancy test (for women of childbearing potential only)
- Cancer screening should be conducted per the current American Cancer Society Guidelines for the Early Detection of Cancer. Testing should also include: pap smear and mammogram if not performed within past 12 months (females only); chest X-ray or chest CT scan (if the subject has a previous history of tobacco use, a CT scan will be performed instead of X-ray) within 3 months prior to study entry; PSA within past 3 months (males only);[†] for subjects ≥ 50 years old, colonoscopy within past 10 years; for subjects with family history of colon cancer in any first degree relative, colonoscopy within past 12 months.
- Viral screening – HIV, Anti-Human T-Cell Lymphotropic Virus (HTLV), Positive Hepatitis B or C as determined by Hepatitis B core antibody (HBcAb), antibody to Hepatitis B antigen (IgG and IgM; HBsAb), Hepatitis B surface antigen (HBsAg) and Hepatitis C antibodies (Anti-HCV), at Screening
- Retinal Fundoscopy – in cases where fundoscopy alone is deemed insufficient to rule out exclusionary conditions (see exclusion criterion # 12), fluorescein angiography may be conducted

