4.2.12. BRIEF PERIPHERAL NEUROPATHY SCREENING (BPNS)

Symptoms of BPNS will be assessed at pre-screening and Month 6 in order to evaluate the bilateral extent of DPN (see [Appendix 10](#)).

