1. SYMPTOMS**PRESENCE/SEVERITY**

	Right	Left
a. Pain, aching, or burning in feet, legs:		
b. "Pins and needles" in feet, legs:		
c. Numbness (lack of feeling) in feet, legs:		
d. Total points (add a + b +c):		

AT SCREENING, THE DIFFERENCE BETWEEN LEGS SHOULD BE \leq 5 POINTS IN ORDER TO BE ELIGIBLE.

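### The BPNS form does not say how code 11 (always normal) is scored; if added as written, an unmatched 11 makes the 5-point between-leg rule reject balanced legs and accept unbalanced ones

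*Protocol*

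**What the plan says.** Appendix 10 of the protocol has the subject rate pain (item a), tingling (b) and numbness (c) "on a scale of 01 (mild) to 10 (most severe) for right and left feet, legs". Two further codes go in the same column: 00 for a symptom present in the past but not since the last visit, and 11 for one that never occurred ("If the symptom has never been present, enter '11-Always Been Normal"). The last line of the form is "Total points (add a + b +c"), completed separately for right and left. Beneath it stands the eligibility note: "AT SCREENING, THE DIFFERENCE BETWEEN LEGS SHOULD BE" no more than 5 points.

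The same limit is inclusion criterion 6 (Protocol 3.3.1), a "point difference between legs at Initial Screening" of at most 5. It is also one of the conditions in Protocol 3.4.3 that must be met before full screening begins ("point difference in symptom of BPNS between legs"). Protocol 4.2.12 gives the purpose of the instrument: to "evaluate the bilateral extent of DPN". SAP 11.3.6 summarises the BPNS total at Screening and Month 6, and its change, as continuous variables. None of these places says what 11 contributes to a sum.

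**The concern.** The number 11 is a status label, but it is entered where severities are entered and the only written instruction is to add the entries. The best possible state, a symptom never experienced, then counts for more than the worst severity of 10.

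The between-leg rule exists to admit subjects with similar symptoms on both sides. If 11 is added and appears in one leg only, the rule can do the opposite. With up to 20 sites and no written scoring rule, the same answers could also be accepted at one site and rejected at another.

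Criterion 3 ("Diagnosis of painful diabetic peripheral neuropathy in both lower extremities") makes an 11 on the pain item unlikely, so in practice this concerns tingling and numbness. The same total feeds the change score in SAP 11.3.6, where a new symptom could register as an improvement.

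**Working it through.** The plan states no figure to reproduce here; the check is of the scoring rule itself.

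**Inputs (Protocol Appendix 10).** Each item is 0, 1 to 10, or code 11. Leg total = a + b + c. The subject is eligible on this rule if |right - left| <= 5. Assumption: a symptom never present has zero severity.

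**Step 1: general result.** Let T be the total of the leg holding the 11 minus the total of the other leg, with 11 scored as 0. With one 11 not offset in the other leg, literal addition records T + 11.

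- Accepted with 11 as 0: -5 <= T <= 5.
- Accepted with 11 added: -5 <= T + 11 <= 5, that is -16 <= T <= -6.

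| T (11 as 0) | Recorded (11 added) | 11 as 0 | 11 added |
|---|---|---|---|
| -17 or below | -6 or below | reject | reject |
| -16 to -6 | -5 to +5 | reject | accept |
| -5 to +5 | +6 to +16 | accept | reject |
| +6 or above | +17 or above | reject | reject |

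The two acceptance ranges do not overlap, so no answer pattern passes under both readings. Equal numbers of 11s in the two legs cancel and do no harm.

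**Step 2: other two items equal between legs.** If the other leg scores s on the affected item, the recorded difference is 11 - s; with 11 as 0 its size is s.

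- s = 0 to 5: recorded 11 to 6, rejected; with 11 as 0 it is 0 to 5, accepted.
- s = 6 to 10: recorded 5 to 1, accepted; with 11 as 0 it is 6 to 10, rejected.

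All 11 values of s reverse (6 one way, 5 the other). If the other items differ by d (leg with the 11 minus other leg), the cut moves but the reversal remains. For d = +2, literal addition accepts s = 8 to 10, and 11 as 0 accepts s = 0 to 7. For d = -2, the ranges are 4 to 10 and 0 to 3.

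**Step 3: two subjects.**

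- Right 2, 2, never; left 5, 5, 9. Literal: |15 - 19| = 4, accepted. 11 as 0: |4 - 19| = 15, rejected.
- Right 6, 5, never; left 4, 4, 8. Literal: |22 - 16| = 6, rejected. 11 as 0: |11 - 16| = 5, accepted.

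**Step 4: enumeration.** Take item a from 1 to 10 and item b from 0 to 10 in each leg, with item c never present in one leg and 0 to 10 in the other. This gives 10 x 10 x 11 x 11 x 11 = 133,100 patterns, with T from -29 to +19.

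- Accepted only with 11 as 0: 61,927 (46.5%).
- Accepted only with 11 added: 56,652 (42.6%).
- Rejected under both: 14,521 (10.9%).
- Accepted under both: 0.

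These are unweighted counts of possible answers, given that an unmatched 11 is present. They are not patient rates.

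**Step 5: SAP 11.3.6.** An item never present in either leg adds 11 + 11 = 22 to a two-leg total, against 10 + 10 = 20 for the worst severity. An item coded 11 at Screening and s at Month 6 contributes s - 11 to that leg's change instead of +s: -10 to -1 for s = 1 to 10, and -11 for s = 0. If items a and b each worsen by 2 as well, the leg change is 4 + 4 - 11 = -3 for s = 4, or 4 + 10 - 11 = +3 for s = 10. With 11 as 0 these would be +8 and +14. An item coded 11 at both visits contributes 0, which is correct.

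**The case against.** The strongest reply is that no sensible coordinator would add 11. On the printed scale 11 stands beside 00 at the symptom-free end, not above 10, and its label plainly means normal. Nothing in the documents shows that any site would add it or that sites would differ, and separate form-completion instructions, if they exist, are not among these documents. This limits what can be claimed to a possible misclassification. It does not supply a rule, and the one instruction on the page is to add the entries.

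The pattern also needs a subject with painful neuropathy in both legs who has never had tingling (or numbness) in one leg but has a 0 to 10 entry for it in the other. Protocol 1.7 calls the disease bilateral by definition and Protocol 1.1.2 describes symptoms as often symmetric, so it may be uncommon. That stands; the frequency is not given. But the 5-point rule is there to catch asymmetric subjects, and those are the subjects in whom an unmatched 11 can arise.

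The consequences are also limited, and this stands in full. The rule acts before randomisation, and a subject let through must still meet the VAS, MNSI, diary and bilateral-diagnosis criteria. BPNS is listed only among the other efficacy measures in the synopsis; it is absent from the secondary endpoints in Protocol 6.3.2 and has no table in SAP Appendix A. The change-score error needs a symptom to appear for the first time after Screening.

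**Conclusion.** The concern holds. Followed as written, Appendix 10 scores a never-present symptom above the worst severity, and no section of the protocol or SAP corrects this. For a subject with one unmatched 11, eligibility under literal addition and eligibility with 11 as 0 are mutually exclusive: differences of up to 5 points are rejected, and anyone accepted has a difference of 6 to 16 points.

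Calling these decisions wrong assumes that never present means zero severity, which the label supports but the documents do not state. Whether any subject is affected depends on how sites score 11 and how often the pattern occurs; neither is known. The randomised comparison and the primary diary endpoint are not affected, and the effect on the BPNS change score is minor. It should be corrected because it makes a hard entry criterion ambiguous and costs almost nothing to settle.

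**What to change.** Add one scoring sentence to Protocol Appendix 10 and to SAP 11.3.6: code 11 is scored as 0 when totalling items a, b and c, when computing the between-leg difference, and when computing the change from Screening to 6 months. Check eligibility on the recoded totals. SAP 11.3.6 should also say whether the analysed total is per leg or over both legs; either is acceptable.

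The cost is that sentence in two documents and a recode in programming. No new data are needed, and the entered code can still be kept to separate never present from currently absent.
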